Women under age 21 are excluded because they cannot legally buy cigarettes. Those with unstable medical, psychiatric, or medication conditions (condition and/or medication changes in the past three months) are excluded as these symptoms could affect a participant's ability to complete the study. Examples include but are not limited to the following: angina, stroke, heart attack which occurred since phone screening, blood clots in the arms or legs for which the individual is undergoing active medical treatment, cancer requiring active chemotherapy or radiation therapy, severe shortness of breath caused by conditions such as uncontrolled asthma, COPD, or arrhythmia, active untreated infection such as pneumonia, active untreated endocrine disorder such as hyperthyroidism. Individuals with baseline CO readings greater than 50 ppm, those with blood pressure or heart rate readings that are out of range (acceptable ranges are systolic: 80-139 mmHg; diastolic: 50-89 mmHg; heart rate: 45-109 bpm) and anyone who has attempted suicide in the past 6 months will be excluded from the study for safety concerns. Individuals who smoke 'roll your own' cigarettes exclusively will be excluded from the study because we will be unable to standardize their baseline smoking behavior. Individuals who have recently participated in a research study will be excluded as participation may have changed their smoking behavior, which may preclude a stable smoking baseline. Because participants are required to complete portions of the protocol independently, they will need to be able to independently read and comprehend the study materials.

Eligibility Determination:

The research assistant will review the entire screening assessment battery for initial eligibility determination, confirming the subject meets the above described inclusion/exclusion criteria. The final eligibility of the participant will be determined by a licensed medical professional (MD, DO, NP, PA, Master's prepared RN or CRN) at each site after reviewing the Medical History Questionnaire, BDI, Mini Neuropsychiatric Interview, and the MINI suicide subscale. The licensed medical professional may meet with a participant if available and think it necessary for eligibility determination. He/she will sign off on

eligibility prior to the first baseline visit. If the licensed medical professional determines the participant is not medically eligible to participate in the study, has current symptomatology that would interfere with interpretation of the data or is unlikely to complete the study he/she will inform the research assistants who will contact the participant prior to the first baseline visit. The licensed medical professional will not need to review the medical history forms of participants who are not eligible for other, non-medical reasons.

If a participant fails the urine or saliva toxicology screen due to a prescription medication she is taking, then she will not be automatically excluded. The interviewer will make note of this when he/she submits the forms to the licensed medical professional for final eligibility determination.

Once all the screening procedures have been completed, researchers will pay participants \$25 for their time as long as they meet the requirements for urine cotinine. Participants will be paid after the completion of the study visit. If participants are deemed ineligible at any point in the screening, the participant will be paid after they are determined ineligible. Participants who meet all other eligibility criteria, sans the medical criteria, will be scheduled for the first baseline visit.

At the end of the screening session, the researcher will complete the End of Visit Evaluation Form. This will allow the researcher to make note of any problems encountered during the visit and to assess the truthfulness of the participant in regards to self-report of tobacco use.

Study 2 Baseline Procedures

This study will use a one-week, two-session baseline period to collect baseline individual difference measures and monitor daily usual-brand smoking behavior. During the baseline period, participants will not be provided their usual brand cigarettes to smoke. Use of a two session baseline period will ensure stability of daily smoking reports, reduce reactivity to the daily cigarette monitoring, and reduce participant burden. During the two baseline sessions, participants will complete subjective questionnaires. Each visit will last approximately two hours or less. At the end of each baseline session, the researcher will complete the End of Visit Evaluation Form. This will allow the researcher to make note of any problems encountered during the visit and to assess the truthfulness of the participant in regards to self-report of tobacco use.

Participants will also be supplied with urine collection equipment either by curbside pick-up or courier service at time of Screening or Baseline 1 assessment so that they can collect first void urine samples during the Baseline 2 visit.

For the Baseline 1 visit and all subsequent visits, the participant will be sent a REDCap link within 15 minutes of the start of the scheduled visit to complete all of the non-interviewer administered questionnaires. The participant will complete these questionnaires on their own but can have the research staff member present on a video call if they desire. Before beginning the physiological assessment portion of the visit over video call, research staff must review the participant's questionnaire responses for that visit. Participants will be compensated after the completion of the study visit and when the participant has received their new product.

At Baseline 2 and all subsequent visits, after the participant has answered the questionnaires and has completed the physiological portion of the visit over video call, they will be asked to come to the lab for exchange of product and biological samples. Participants will bring in their used and unused product from

the previous visit (starting at Week 1). Additionally, first-void urine samples will be collected at Baseline 2, Week 6, and Week 12 for assessing tobacco-related toxin exposure. Participants will be instructed to call staff at the office when they get to the clinic to ensure that there is enough space in the smoking chambers to house all participants while abiding by safety guidelines as detailed on page 14 of the protocol. All participants must pass a COVID19 screening before entering the building. When invited into the lab, the participant will be shown to a smoking chamber and will be instructed to place their bag of product outside of the chamber. The participant will wait here while the staff processes and returns product through the randomization database. Staff will dispense new product and bring the bag back to the participant. When the RA deems it safe for the participant to exit the chamber, the RA will instruct the participant that they can leave. The RA will instruct the participant to observe social distancing measures during this exchange, providing clarification if necessary. If a participant forgets their first-void urine sample at the Baseline 2 visit, staff will ask participant to come back to the clinic with their first void urine sample before exchange of product occurs. If participant is unable to return to the clinic with their first void sample, staff can arrange to meet the participant off campus to pick up their urine sample and to give participant their study product. Distancing and safety measures as described above must be observed. For participants who cannot make it to UHC, special arrangements will be made to enable use of the randomization database and product return/distribution procedures to the extent possible. Each week, during - or scheduled as nearly as possible to – a virtual visit, a complete accounting of the participant's product inventory will be taken and processed remotely through the randomization database. The participant will separate product based on its status (used/unused), and staff will process return characteristics through the database accordingly. Staff will clarify barcode characteristics with the participant when legibility is compromised. When the exchange is done via courier, the participant will be instructed to keep unused product in their possession, but to exchange any used product with the courier who will deliver newly dispensed replacement products within 48 hours.

Product that will be given to participants for the Baseline 2 visit cannot be given/sent to participants until 7 days have passed following completion of the Baseline 1 visit. We will need to calculate baseline smoking rate during this 7-day period and so participants cannot have access to any study product before this 7-day period has ended.

Visit scheduling requirements for baseline period:

Participants will be required to schedule the Baseline 1 visit within 30 days of the completion of their screening visit. If a participant still wants to be in the study after 30 days, she will need to be re-screened. The participant will need to be re-consented but will maintain the original REDCap Subject Identifier. The ideal target window separating Baseline 1 and Baseline 2 is between 7 and 12 days. The minimum is 7 days and the maximum is 21 days. If the participant does not complete the visit within 21 days, then she will not be rescheduled and will be discontinued from the study.

Measures/Assessments

The following physiological measures will be collected at Baseline 1 and recorded directly into REDCap by the interviewer:

- 1) CO
- 2) Blood pressure
- 3) Heart rate

The following assessments will be administered as an interview at Baseline 1 and entered directly into REDCap by the interviewer:

- 1) Concomitant Medications Form
- 2) Time Since Last Cigarette Questionnaire
- 3) Health Changes Questionnaire, which will assess any weekly health changes
- 4) Maintenance Drug Dose Questionnaire (if applicable)

The following assessments will be administered at Baseline 1 and completed by the participant directly in REDCap:

- 1) BDI
- 2) OASIS
- 3) Perceived Health Risks Rating (Hatsukami et al., 2010), a measure of the perceived addictive potential and other health risks associated with cigarettes
- 4) Respiratory Health Questionnaire, a measure of cough, shortness of breath and other respiratory symptoms
- 5) Minnesota Nicotine Withdrawal Scale (MNWS; Hughes & Hatsukami, 1986), a measure of nicotine withdrawal
- 6) Questionnaire of Smoking Urges-brief scale - Usual Cigarette (QSU-brief; Cox, Tiffany, & Christen, 2001; Tiffany & Drobes, 1991), which measures the urge to smoke
- 7) Cigarette Evaluation Scale – Usual Cigarette (CES; Westman, Levin, & Rose, 1992), which measures responses to cigarettes (e.g., reward, satisfaction)
- 8) Intolerance for Discomfort Questionnaire (IDQ; Sirota et al., 2013), assesses intolerance for the discomfort of smoking abstinence. The measure includes three subscales: physical discomfort, emotional discomfort and smoking withdrawal discomfort.
- 9) Cigarette Purchase Task - Usual Brand Version (CPT; MacKillop et al., 2008), a self-report analogue of a progressive-ratio schedule that measures the relative reinforcing efficacy of cigarettes by querying how many of that day's cigarette they would consume in a day at varying prices. This task will indicate whether prolonged VLNC cigarette use reduces cigarette demand and increases sensitivity to increases in cigarette costs.
- 10) Perceived Stress Scale - 4 item (PSS-4; Cohen, Kamarck, & Mermelstein, 1983), which measures the degree to which life situations are appraised as stressful
- 11) Positive and Negative Affect Schedule (PANAS; Watson, Clark, & Tellegan, 1988), which measures symptoms of positive and negative affect
- 12) Pregnancy-Unique Quantification of Emesis Scale – 24 hour (PUQE-24; Ebrahimi et al., 2009), which assesses severity of nausea and vomiting specific to pregnancy.
- 13) COVID-19 Symptom Questionnaire

The following Baseline 2 physiological measures will be collected and recorded directly into REDCap by the interviewer:

- 1) CO
- 2) Blood pressure
- 3) Heart rate

The following assessments will be administered as an interview at Baseline 2 and then entered directly into REDCap by the interviewer:

- 1) Concomitant Medications Form
- 2) Time Since Last Cigarette Questionnaire
- 3) Health Changes Questionnaire
- 4) Maintenance Drug Dose Questionnaire (if applicable)

The following assessments will be administered at Baseline 2 and completed by the participant directly in REDCap:

- 1) BDI
- 2) OASIS
- 3) FTND
- 4) WISDM-brief
- 5) PUQE-24
- 6) COVID-19 Symptom Questionnaire

In the event that the REDCap website is not functioning, the assessments will be administered aloud and participant answers will be recorded securely. The interviewer will enter the data into REDCap when it resumes functioning properly. A note indicating that REDCap was not functioning during the session should be recorded in the 'End of Visit Evaluation Form'.

Interactive Voice Response System:

At the end of the first baseline visit, participants will be trained to use the Interactive Voice Response (IVR) System, which will contact participants each day throughout the study and ask about their smoking behavior as well as withdrawal symptoms the week before and after randomization. We will also review the IVR adherence incentive program, which consists of \$1 per call plus a \$10 bonus for seven consecutive calls. Participants may be provided a study cell phone if they have unreliable telephone access, do not have enough monthly cell phone minutes or prefer not to use their own phone.

The IVR system is operated by TeleSage. To be enrolled in the IVR system, research staff will enter the participant's initials, telephone number, subject identifier, and visit dates into the IVR TCORS website. Identifying information (initials and telephone numbers) will not be extracted with the data by the bioinformatics group. Please refer to TeleSage's privacy statement and HIPAA compliance form for additional information.

Baseline 2 biological specimens:

- 1) Urine sample for smoking biomarker assessment:

Participants will be asked to provide a urine sample (first void of the day) at the second baseline session for biomarker assessment. Samples will be stored at temperatures no more than -80°C. The tobacco-specific carcinogen biomarkers are total NNAL and PAH. Total cotinine levels will also be assessed to measure daily nicotine exposure. Participants will be reminded with a phone call the day before the visit, those who forget will be asked to return to the lab with their first void

urine sample or staff can arrange to meet the participant off campus to pick up their urine sample.

Biomarker shipping and storage:

Biomarkers will be shipped quarterly to the University of Vermont Laboratory for Clinical Biochemistry Research ([name] Lab). The [name] Lab will serve as a central repository for all biomarker specimens and will be responsible for distributing specimens to the appropriate labs on a quarterly basis. Urine samples will be analyzed and stored at the University of Minnesota [name] Lab.

Study 2 Experimental Procedures

Experimental Period:

Participants will be seen weekly throughout the 12-week experimental period. Study Weeks 2, 6, and 12 will take approximately 2-4 hours each. All other sessions will last 1-2 hours. As a part of each experimental visit, participants will be asked to come to UHC for a product exchange. All participants must pass a COVID19 screening before entering the building. Participants will be instructed to contact the RA at the office when they get to the clinic to ensure that there is enough space in the smoking chambers to house all participants while abiding by safety guidelines as detailed on page 14 of the protocol. When invited into the lab, the participant will be shown to a smoking chamber and will be instructed to place their bag of product outside of the chamber. The participant will wait here while the RA processes and returns product through the randomization database. Then the RA will dispense new product and bring the bag back to the participant's smoking chamber and leave it on the ground in front of the chamber. When the RA deems it safe for the participant to exit the chamber, the RA will instruct the participant that they can leave. The RA will instruct the participant to observe social distancing measures during this exchange, providing clarification if necessary.

Visit scheduling requirements for experimental period:

The ideal scheduling window between each visit is 7 days based on the date of the Baseline 2 (randomization) Visit. For additional scheduling requirements, refer to the '*Scheduling Visits SOP*'. If a participant misses a visit and is not able to reschedule during the window (\pm 3 days), that visit will not be 'made-up' in the future. All measures that were not completed will be considered missing data and will not be collected during future visits. If a visit mistakenly occurs outside of the designated window, this is a protocol deviation. A 'Non-Medical Event Form' will need to be completed. Additionally, each visit should occur at approximately the same time of day \pm 1 hours.

If a participant is not able to attend her Week 12 visit, then it should be rescheduled even if it is outside of the scheduling window. This will be documented as a protocol deviation.

Experimental Visits: Study Weeks 1, 3, 5, 7, 9, and 11:

Measures/Assessments

Physiological Measures will be collected and entered directly into REDCap by the interviewer:

- 1) CO
- 2) Blood pressure
- 3) Heart rate

The following assessments will be administered as an interview and will be entered directly into REDCap by the interviewer:

- 1) Concomitant Medications Form
- 2) Time Since Last Cigarette Questionnaire
- 3) Health Changes Questionnaire
- 4) Medical Event Form (if applicable)
- 5) Maintenance Drug Dose Questionnaire (if applicable)

The following assessments will be completed by the participant directly in REDCap:

- 1) BDI
- 2) OASIS
- 3) MNWS
- 4) QSU brief – with reference to assigned cigarette
- 5) CES – with reference to assigned cigarette
- 6) PUQE-24
- 7) COVID-19 Symptom Questionnaire

In the event that the REDCap website is not functioning, the assessments will be administered aloud and participant answers will be recorded securely. The interviewer will enter the data into REDCap when it resumes functioning properly. A note indicating that REDCap was not functioning during the session should be recorded in the 'End of Visit Evaluation Form'.

Experimental Visits: Study Weeks 2, 4, 6, 8, 10 & 12:

Measures/Assessments

Physiological measures will be collected and entered directly into REDCap by interviewer:

- 1) CO
- 2) Blood pressure
- 3) Heart rate

The following assessments will be administered as an interview and will be directly entered into REDCap by the interviewer:

- 1) Concomitant Medications Form
- 2) Time Since Last Cigarette Questionnaire
- 3) Health Changes Questionnaire
- 4) Medical Event Form (if applicable)
- 5) Maintenance Drug Dose Questionnaire (if applicable)

The following assessments will be completed by the participant directly in REDCap:

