The research assistant will review the entire screening assessment battery for initial eligibility determination, confirming the subject meets the above described inclusion/exclusion criteria. The final eligibility of the participant will be determined by a licensed medical professional (MD, DO, NP, PA, Master's prepared RN or CRN) at each site after reviewing the Medical History Questionnaire, BDI, Mini Neuropsychiatric Interview, and the MINI suicide subscale. The licensed medical professional may meet with a participant if available and think it necessary for eligibility determination. He/she will sign off on eligibility prior to the baseline visit. If the licensed medical professional determines the participant is not medically eligible to participate in the study, has current symptomatology that would interfere with interpretation of the data or is unlikely to complete the study he/she will inform the research assistants who will contact the participant prior to the baseline visit. The licensed medical professional will not need to review the medical history forms of participants who are not eligible for other, non-medical reasons.

Once all the screening procedures have been completed, researchers will pay participants \$25 for their time as long as they meet the requirements for urine cotinine levels. Those participants who do not meet these requirements will be dismissed from the study without payment. Participants who meet all other eligibility criteria, sans the medical criteria, will be scheduled for the baseline visit.

At the end of the screening session, the researcher will complete the End of Visit Evaluation Form, which will be filed in the subject's binder. This will allow the researcher to make note of any problems encountered during the visit, to track which computers were used for which tasks, and to assess the truthfulness of the participant in regards to self-report of tobacco use.

Study 1 Baseline Procedures

During the baseline session (Session 1), participants will become acquainted with the general study procedures, equipment, use of the CReSS Desktop smoking topography device (Borgwaldt, Richmond, VA) and controlled puffing regimens, and subjective effects questionnaires. Participants will arrive at the baseline visit having abstained from smoking sufficiently to achieve a breath CO level that is \leq 50% of their baseline level (approximately 6-8 hours). The CO level obtained at Screening will be considered the baseline level.

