- 2) Complete the Cigarette Purchase Task (CPT; MacKillop et al., 2008), a self-report analogue of a progressive-ratio schedule that measures the relative reinforcing efficacy of cigarettes by querying how many of that day's cigarette they would consume in a day at varying prices.
 - a. Will be entered directly into REDCap by the participant.
- 3) Complete the CES (CES; Westman, Levin, & Rose, 1992), which measures responses to cigarettes (e.g., reward, satisfaction)
 - a. Will be entered directly into REDCap by the participant.

In the event that the REDCap website is not functioning, the assessments will be printed out and administered on paper. The source documents will be kept in the participant's binder. The interviewer will enter the data into REDCap when it resumes functioning properly. This information should be recorded in the 'End of Visit Evaluation Form' and filed in the participant's binder.

Study 1 Experimental Procedures

Study 1 will be conducted in three phases at approximately 3 sessions per week. Participants will arrive at each experimental session having abstained from smoking sufficiently to achieve a breath CO level that is \leq 50% of their baseline level (approximately 6-8 hours), an abstinence criterion that has been used widely in tobacco research (e.g., Johnson et al., 2004; Tidey et al., 1999). Upon arrival at the laboratory, participants will provide a breath CO sample, complete questionnaires querying time since last cigarette, ratings of craving and withdrawal (measured using the QSU and MNWS), and update medical and medication information since the previous session. Should a participant not meet the CO abstinence criterion, the session will be rescheduled. Those who meet the CO criterion will then take two puffs from their usual brand cigarette, which is a commonly used procedure to equate time since last cigarette across sessions (e.g., Johnson et al., 2004; Henningfield & Griffiths, 1981). Thirty minutes after those initial puffs, the experimental session will commence. During these sessions, participants cannot eat or drink anything other than water.

Visit scheduling requirements for experimental period:

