- 2) CO (must be \leq 50% of the level taken at screening)
- 3) Blood Pressure
- 4) Heart Rate

The following assessments will be administered as an interview and then entered into REDCap by the interviewer at the end of the visit, except where noted:

- 1) Concomitant Medications
- 2) Medical Event Form, if applicable
- 3) Health Changes Questionnaire
- 4) Ratings of Craving and Withdrawal (measured using the QSU and MNWS)
 - a. Will be entered directly into REDCap by the participant.
 - b. Done at the beginning of each session.
- 5) Time Since Last Cigarette Questionnaire

After finishing the cigarette, participants will:

- 1) Provide breath CO samples and rate craving/withdrawal every 15 minutes for one hour.
 - a. The first CO sample should be taken 15 minutes after finishing the cigarette and then every 15 minutes thereafter for one hour.
 - b. The participant will enter craving and withdrawal ratings directly into REDCap.
- 2) Complete the Cigarette Purchase Task – Study Cigarette
 - a. Will be entered directly into REDCap by the participant.
- 3) Complete the CES – Study Cigarette
 - a. Will be entered directly into REDCap by the participant.

Phase 2

In Phase 2, Sessions 5-7 will compare reinforcing effects of the various nicotine-dose cigarettes when they are available at equally low response costs. Using equipment and methods that we have used previously to study reinforcing efficacy of smoking (Sigmon et al., 2003; Tidey et al., 1999), the reinforcing efficacy of two nicotine doses will be compared in each session. During these 3-hr sessions, participants will make 10 keyboard presses to obtain 2 puffs of either cigarette; there is no limit to the number of choices of either cigarette type in a session; this is a commonly used very-low-effort fixed- ratio response requirement (Lussier et al., 2005; Yoon et al., 2009; Tidey et al., 1999). Each dose pair will be evaluated once per participant, in random order and under double-blind conditions (save for comparisons involving usual brand cigarettes).

Measures/Assessments

Physiological Measures Collected, recorded on paper, and entered into REDCap by interviewer at the end of the visit:

- 1) Weight
- 2) CO (must be \leq 50% of the level taken at screening)
- 3) Blood Pressure
- 4) Heart Rate

The following assessments will be administered as an interview and then entered into REDCap by the interviewer at the end of the visit, except where noted:

- 1) Concomitant Medications

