- 2) Medical Event Form, if applicable
- 3) Health Changes Questionnaire
- 4) Ratings of Craving and Withdrawal (measured using the QSU and MNWS)
 - a. Will be entered directly into REDCap by the participant.
 - b. Will be done at the beginning and end of each session.
- 5) Time Since Last Cigarette Questionnaire

Phase 3

In Phase 3, Sessions 8-9 will examine the extent to which the lowest nicotine dose (0.03 mg) functions as a substitute for the usual brand dose when the response cost for the usual brand dose progressively increases (Johnson et al., 2004). Again, doses will be tested in pairs. In these 3-hr sessions, 2 puffs of the lower-nicotine cigarette will be available at a constant low response requirement (10 keyboard presses), while 2 puffs of the usual brand cigarette will be available on a progressive-ratio schedule that begins at 10 presses and increases each time it is chosen, using a progression used in our prior studies (160, 320, 640, 1280, 2400, 3600, 4800, 6000, 7200, 8400, etc.) (Sigmon et al., 2003; Tidey et al., 1999). There is no limit to the number of choices of either cigarette type in a session. We will calculate cross-price elasticity for each dose to quantify the degree to which it serves as an economic substitute for the usual brand cigarette (Johnson et al., 2004).

Measures/Assessments

Physiological Measures Collected, recorded on paper, and entered into REDCap by interviewer at the end of the visit:

- 1) Weight
- 2) CO (must be \leq 50% of the level taken at screening)
- 3) Blood Pressure
- 4) Heart Rate

The following assessments will be administered as an interview and then entered into REDCap by the interviewer at the end of the visit, except where noted:

- 1) Concomitant Medications
- 2) Medical Event Form, if applicable
- 3) Health Changes Questionnaire
- 4) Ratings of Craving and Withdrawal (measured using the QSU and MNWS)
 - a. Will be entered directly into REDCap by the participant.
 - b. Will be done at the beginning and end of each session.

- 5) Time Since Last Cigarette Questionnaire
- 6) Cigarette Purchase Task – Study Cigarette
 - a. Two CPTs will be completed (one for each cigarette type).
 - b. Will be entered directly into REDCap by the participant.

Participant Compensation:

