Any SAE will be brought to the attention of the site PIs as soon as possible and not longer than 24 hours. Any AE or SAE that is both unexpected and related to study participation will be reported to the IRB within 7 days of the event. The IRB will make a determination as to whether additional reporting requirements are needed. IRB actions will be reported to the funding agency by the PIs no less than annually and more frequently as recommended by the local IRB. Any SAEs will be summarized in the yearly Progress Reports to the funding agency, including a review of frequency and severity. All SAEs will be followed through ongoing consultation with the physician caring for the patient until they resolve, result in death, or stabilize and are not expected to improve. The study staff will be in close contact with participants and health care providers throughout the study to monitor for potential unanticipated problems. Any unanticipated problems will be discussed at the weekly research staff meetings and reported as required to the local IRB.

Withdrawal or Monitoring of Participants

For the participant's protection, participants will be withdrawn immediately from the study if any of the following occur:

- 1) Pregnancy complication: Typically includes miscarriage, stillbirth, or preterm delivery.
- 2) Cardiovascular disease (CVD) event: Typically includes MI (heart attack), PTCA (angioplasty/stenting), bypass surgery, stroke, peripheral vascular disease (arterial blockages in arms or legs leading to procedure or surgery). Less common CVD problems would be new cardiac arrhythmias (e.g., new atrial fibrillation) or new valvular disease (e.g., mitral or aortic regurgitation).
- 3) Deep vein thrombosis (DVT)/pulmonary embolism (PE): I.e., blood clots in the venous system.
- 4) Suicide attempt: A participant will be withdrawn if she attempts suicide at any time during participation in the study.
- 5) Psychiatric hospitalization: A participant will be withdrawn if she is hospitalized for psychiatric reasons at any time during participation in the study.

- 6) Expired breath CO increase: A participant will be withdrawn from the study if the average of two consecutive CO readings during the same visit is more than double their Baseline exhaled CO measurement, or greater than 50 ppm at any given time.

The following will be monitored and can lead to the participant being withdrawn by the PI or Licensed Medical Professional:

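### In Study 1 Sessions 5-9, the only scheduled breath CO is the arrival reading, so scheduled readings cannot show whether smoking in the session breached the CO withdrawal rule

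*Protocol*

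**What the plan says.** **Smoking.** Under Study 1 Experimental Procedures, Phase 2 (Sessions 5-7) offers two puffs of either cigarette for 10 key presses over three hours, and "there is no limit to the number of choices of either cigarette type in a session". Phase 3 (Sessions 8-9) keeps the low-dose cigarette at 10 presses and puts the usual brand on a rising ratio. It repeats the condition: "There is no limit to the number of choices of either cigarette type in a session".

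**CO in those sessions.** The general text on experimental sessions places CO first: "Upon arrival at the laboratory, participants will provide a breath CO sample". The two equalising puffs come after it, and the session starts 30 minutes later. The arrival value is a gate: "Should a participant not meet the CO abstinence criterion, the session will be rescheduled". The Phase 2 and Phase 3 measurement lists each carry one CO entry, labelled with this abstinence limit. Study 1 Baseline Procedures fixes the reference: "The CO level obtained at Screening will be considered the baseline level". Craving and withdrawal ratings are repeated in these phases: "Will be done at the beginning and end of each session". That note stands under the ratings and not under CO.

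**CO elsewhere in Study 1.** The baseline session and Phase 1 take CO every 15 minutes for one hour after the cigarette.

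**The rule.** Withdrawal or Monitoring of Participants lists events that require immediate withdrawal for the participant's protection. Item 6 applies if "the average of two consecutive CO readings during the same visit is more than double their Baseline exhaled CO measurement", or if CO is above 50 ppm at any time. Study 1 is not exempted. The SAP covers only the extended-exposure study and does not address this.

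**The concern.** A mandatory protection works only if the schedule produces the measurement it depends on. Here CO is followed after one ad lib cigarette and one practice cigarette (Phase 1), but not after three hours in which the number of choices is uncapped. Staff who follow the plan exactly would have no scheduled means of knowing whether a participant had met the CO criterion through smoking in Sessions 5-9.

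The protocol itself treats smoke exposure in pregnancy as a central worry. Its background section promises close monitoring of puff topography and exposure markers, and CO is a listed exposure measure in the endpoints shared by both studies. At stake is whether the study can later say that its CO rule was applied throughout Study 1.

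**Working it through.** The plan gives no figure to reproduce. The check sets the schedule of readings against the two limbs of the rule.

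**Inputs**
- Largest baseline CO, B: 50 ppm (Study 1 exclusion criterion 5 removes anyone above 50).
- Baseline for Study 1: the screening CO (Study 1 Baseline Procedures).
- Arrival CO needed to proceed: at most 0.5 × B (Study 1 Experimental Procedures).
- Limb 1: mean of two consecutive same-visit readings above 2 × B. Limb 2: any reading above 50 ppm (item 6 of the immediate-withdrawal list).
- Experimental sessions: 2-4 (Phase 1), 5-7 (Phase 2), 8-9 (Phase 3), eight in all.

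**Scheduled CO readings after smoking starts**

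| Session | Smoking | Post-smoking CO |
|---|---|---|
| 1 (baseline) | limited | 4 |
| 2-4 | one ad lib and one practice cigarette | 4 each |
| 5-7 | 3 h, no cap on choices | 0 |
| 8-9 | 3 h, no cap; usual brand on rising ratio | 0 |

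**Can the arrival reading meet either limb in a session that proceeds?**
- Largest arrival value: 0.5 × 50 = 25 ppm. Against limb 2: 25 / 50 = one half.
- Against limb 1: 0.5B / 2B = one quarter, whatever B is.
- The lower of the two triggers is 2B when B is 25 ppm or less, and 50 ppm when B is above 25. The arrival value is therefore at most one quarter of the lower trigger for B up to 25, rising to one half at B = 50.

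So the arrival reading cannot meet either limb in a session that goes ahead. It is also taken before any session smoking. A high arrival value would reflect smoking before the visit, and the session would be rescheduled.

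**Can a later reading stand in?** No. Sessions 3-9 are at least every other day, and each next arrival again follows abstinence to half of baseline or below.

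**Extent.** 5 of 8 experimental sessions; 5 × 3 h = 15 session hours per participant.

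**The case against.** The best reply is that there is no contradiction. The withdrawal list is generic to both studies and says what to do if a high CO is seen; the Phase 2 and 3 lists merely say what is collected. Blood pressure and heart rate are listed at these sessions with an out-of-range procedure, and adverse events are asked about at every visit. That is fair as far as it goes. It does not explain why CO is followed after limited smoking and not here, and the documents give no reason.

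Several stronger readings are tempting and are not supported:

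- **That the rule can never fire in these sessions.** This is true only of scheduled readings. The 50 ppm limb needs a single reading at any time, and an unscheduled one is neither required nor forbidden.
- **That listing one CO defeats the two-reading limb.** Study 2 visits also list a single CO under the same rule, and the second reading may be a confirmatory repeat. The timing of the reading matters more than the count.
- **That exposure goes unmeasured.** The number of puffs chosen is the Phase 2 outcome, and the protocol says the controlled puffing practised in Phase 1 is used in later phases.
- **That the compensatory-smoking question is lost.** The protocol assigns that question to Phase 1, with puff topography and filter analysis as its measures.
- **That intake is wholly unrestrained.** Every pair of puffs costs key presses, and in Phase 3 the usual brand becomes progressively dearer. Only the low-dose cigarette stays at 10 presses there.
- **That breaches are likely.** Reaching limb 1 from the highest permitted arrival value needs more than a four-fold rise (2 / 0.5 = 4). The documents give no figure on how often that would happen.

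The timing objection also has force. SAP section 4.1 reports in the past tense that 19% of smokers at the Vermont site in the acute-exposure portion used menthol, so Study 1 data were probably in hand. A prospective change may then come too late.

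**Conclusion.** The point holds in a limited form. If the plan is followed exactly, no scheduled CO reading in Sessions 5-9 can detect a rise, caused by smoking in the session, that meets either limb of a mandatory withdrawal rule. The gap is the post-smoking CO reading itself. It shows what the schedule cannot reveal, not that anyone exceeded or would exceed a limit. It is a reconciliation point, not a flaw that undermines Study 1's comparisons.

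The conclusion rests on three readings of the text:
- The single CO entry in the Phase 2 and 3 lists is the arrival sample. Its abstinence label and the general session text both say so.
- The instruction to enter measures into REDCap at the end of the visit concerns data entry and does not call for a second measurement.
- Baseline in the rule means the screening CO. If it meant the Session 1 value, the one-quarter figure would change, but the absence of a post-smoking reading would not.

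**What to change.** Reconcile the Phase 2 and Phase 3 measurement lists with item 6 of the immediate-withdrawal list. Either the schedule should supply the readings the rule is defined on in the sessions where participants smoke, or the protocol should state that the rule is not monitored there and why. Which course to take is for the investigators and the safety board, and the threshold itself is not in question. If readings are added, the repeat craving and withdrawal ratings show that staff already carry out assessments at the end of these sessions, and the values could also be summarised as session exposure.

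If Study 1 is complete, report whether any CO was taken after smoking in Sessions 5-9, and state that scheduled CO did not monitor the rule in those sessions.

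**Cost.** If readings are added: an edit to two lists and a few minutes of breath sampling per session with a monitor already in use. Some participants may then be found to meet the existing rule and be withdrawn. That would draw on a thin allowance: 65 enrolled less 5 pilots is 60, and 15% attrition leaves 0.85 × 60 = 51 against 50 planned completers. For a finished study the cost is a statement in the report.
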